#### 10.3.2 Distribution of Adverse Event Reports

CTEP-AERS is programmed for automatic electronic distribution of reports to the following individuals: Principal Investigator and Adverse Event Coordinator(s) (if applicable) of the Corresponding Organization or Lead Organization, the local treating physician, and the Reporter and Submitter. CTEP-AERS provides a copy feature for other e-mail recipients.

#### 10.3.3 Expedited Reporting Guidelines

Use the NCI protocol number and the protocol-specific patient ID assigned during trial registration on all reports.

**Note: A death on study requires both routine and expedited reporting, regardless of causality as long as the death occurred within 30 days after the last administration of the investigational agent. Attribution to treatment or other cause must be provided.**

Death due to progressive disease should be reported as **Grade 5 “Disease progression”** in the system organ class (SOC) “General disorders and administration site conditions.” Evidence that the death was a manifestation of underlying disease (e.g., radiological changes suggesting tumor growth or progression: clinical deterioration associated with a disease process) should be submitted.

**Phase 1 and Early Phase 2 Studies: Expedited Reporting Requirements for Adverse Events that Occur on Studies under an IND/IDE within 30 Days of the Last Administration of the Investigational Agent/Intervention **

**FDA REPORTING REQUIREMENTS FOR SERIOUS ADVERSE EVENTS (21 CFR Part 312)**

**NOTE:** Investigators **MUST** immediately report to the sponsor (NCI) **ANY** Serious Adverse Events, whether or not they are considered related to the investigational agent(s)/intervention (21 CFR 312.64)

An adverse event is considered serious if it results in **ANY** of the following outcomes:

- 1) Death
- 2) A life-threatening adverse event
- 3) An adverse event that results in inpatient hospitalization or prolongation of existing hospitalization for  $\geq$  24 hours
- 4) A persistent or significant incapacity or substantial disruption of the ability to conduct normal life functions
- 5) A congenital anomaly/birth defect.
- 6) Important Medical Events (IME) that may not result in death, be life threatening, or require hospitalization may be considered serious when, based upon medical judgment, they may jeopardize the patient or subject and may require medical or surgical intervention to prevent one of the outcomes listed in this definition. (FDA, 21 CFR 312.32; ICH E2A and ICH E6).

**ALL SERIOUS** adverse events that meet the above criteria **MUST** be immediately reported to the NCI via electronic submission within the timeframes detailed in the table below.

Hospitalization	Grade 1 and Grade 2 Timeframes	Grade 3-5 Timeframes
Resulting in Hospitalization $\geq$ 24 hrs	10 Calendar Days	24-Hour 5 Calendar Days
Not resulting in Hospitalization $\geq$ 24 hrs	Not required	

**NOTE:** Protocol specific exceptions to expedited reporting of serious adverse events are found in the Specific Protocol Exceptions to Expedited Reporting (SPEER) portion of the CAEPR.

**Expedited AE reporting timelines are defined as:**

- "24-Hour; 5 Calendar Days" - The AE must initially be submitted electronically within 24 hours of learning of the AE, followed by a complete expedited report within 5 calendar days of the initial 24-hour report.
- "10 Calendar Days" - A complete expedited report on the AE must be submitted electronically within 10 calendar days of learning of the AE.

Serious adverse events that occur more than 30 days after the last administration of investigational agent/intervention and have an attribution of possible, probable, or definite require reporting as follows:

**Expedited 24-hour notification followed by complete report within 5 calendar days for:**

- All Grade 3, 4, and Grade 5 AEs

**Expedited 10 calendar day reports for:**

- Grade 2 AEs resulting in hospitalization or prolongation of hospitalization

For studies using PET or SPECT IND agents, the AE reporting period is limited to 10 radioactive half-lives, rounded UP to the nearest whole day, after the agent/intervention was last administered. Footnote "1" above applies after this reporting period.

Effective Date: May 5, 2011

#### 10.3.4 Adverse Events of Special Interest

Grade 3 or higher renal and genitourinary AEs will be reported as expedited AEs, including but not limited to:

- Renal failure (ranging from significantly reduced measured or estimated creatinine clearance to clinically overt renal failure other than that of obvious non-investigational agent-induced origin)
- Suspected radiation nephropathy of any type, such as radiation-induced thrombotic microangiopathy, manifesting as:
  - Proteinuria
  - Hypertension
  - Edema
  - Anemia
  - Decreased serum haptoglobin
- General symptoms and signs of acute radiation toxicity, such as:
  - Increased frequency/urgency of urination
  - Nocturia
  - Dysuria
  - Bladder spasm
  - Bladder obstruction
  - Genitourinary ulceration or necrosis

Grade 3 or higher bone marrow toxicities will also be reported as expedited AEs.

#### **10.4 Routine Adverse Event Reporting**

All Adverse Events **must** be reported in routine study data submissions. **AEs reported expeditiously through CTEP-AERS must also be reported in routine study data submissions.**

Adverse event data collection and reporting, which are required as part of every clinical trial, are done to ensure the safety of patients enrolled in the studies as well as those who will enroll in future studies using similar agents. AEs are reported in a routine manner at scheduled times during the trial using Medidata Rave. For this trial the Adverse Event CRF is used for routine AE reporting in Rave.

10.4.1 Clinician graded CTCAE is the AE (adverse event) safety standard. PRO-CTCAE items are to complement CTCAE reporting. Patients will respond to PRO-CTCAE items, but no protocol directed action will be taken. Study specific PRO-CTCAE items for this protocol can be found in Appendix G.

10.4.2 PRO-CTCAE is not intended for expedited reporting, real time review or safety reporting.

10.4.3 Symptomatic Adverse Events reported by patients through PRO-CTCAE are not safety reporting and may be presented with other routine AE data.

10.4.4 PRO-CTCAE Items

Attribute acronyms: F=Frequency, S=Severity, I=Interference, P=Presence/Absence/Amount

CTCAE Item version 5.0	PRO-CTCAE Item (Attributes) version 1.0
Constipation	Constipation (S)
Diarrhea	Loose or watery stools (F)
General Pain	General Pain (FSI)
Fatigue	Fatigue (SI)
Numbness and Tingling	Numbness and Tingling (SI)
Nausea	Nausea (FS)
Vomiting	Vomiting (FS)
Dizziness	Dizziness (FS)
Painful urination	Painful urination (FS)
Urinary urgency	Urinary urgency (FS)
Urinary frequency	Urinary frequency (FS)
Change in urine color	Change in urine color (FS)
Joint pain	Joint pain (FS)

## 10.5 Pregnancy

Although not an adverse event in and of itself, pregnancy as well as its outcome must be documented via **CTEP-AERS**. In addition, the **Pregnancy Information Form** included within the NCI Guidelines for Adverse Event Reporting Requirements must be completed and submitted to CTEP. Any pregnancy occurring in a patient's partner from the time of consent to 90 days after the last dose of study drug must be reported and then followed for outcome. Newborn infants should be followed until 30 days old. Please see the "NCI Guidelines for Investigators: Adverse Event Reporting Requirements for DCTD (CTEP and CIP) and DCP INDs and IDEs" (at [http://ctep.cancer.gov/protocolDevelopment/adverse\\_effects.htm](http://ctep.cancer.gov/protocolDevelopment/adverse_effects.htm)) for more details on how to report pregnancy and its outcome to CTEP.

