- glomerular filtration rate (GFR)  $\geq 50$  mL/min/1.73 m^2 (see Appendix B)

- 3.1.11 Patients receiving bisphosphonates or denosumab prior to enrollment can maintain therapy throughout all or part of the study. The bisphosphonate may be stopped or started at the discretion of the investigator throughout the study (*i.e.*, both treatment phase and follow-up). Injection of bisphosphonates should be done at least 2 hours before or after study drug administration.
- 3.1.12 Human immunodeficiency virus (HIV)-infected patients on effective anti-retroviral therapy with undetectable viral load within 6 months are eligible for this trial.
- 3.1.13 For patients with evidence of chronic hepatitis B virus (HBV) infection, the HBV viral load must be undetectable on suppressive therapy, if indicated.
- 3.1.14 Patients with a history of hepatitis C virus (HCV) infection must have been treated and cured. For patients with HCV infection who are currently on treatment, they are eligible if they have an undetectable HCV viral load.
- 3.1.15 Patients with a prior or concurrent malignancy whose natural history or treatment does not have the potential to interfere with the safety or efficacy assessment of the investigational regimen are eligible for this trial.
- 3.1.16 Patients with known history or current symptoms of cardiac disease, or history of treatment with cardiotoxic agents, should have a clinical risk assessment of cardiac function using the New York Heart Association Functional Classification. To be eligible for this trial, patients should be class 2B or better.
- 3.1.17 The effects of Sn-117m-DTPA on the developing human fetus are unknown. For this reason and because radionuclides are known to be teratogenic, male participants and their female partners must agree to use adequate contraception (hormonal or barrier method of birth control; abstinence) prior to study entry and for the duration of study participation. Should a woman become pregnant or suspect she is pregnant while her male partner is participating in this study, she should inform her treating physician immediately. Men treated or enrolled on this protocol must also agree to use adequate contraception prior to the study, for the duration of study participation, and 6 months after completion of Sn-117m-DTPA administration.
- 3.1.18 Patients must be willing and able to comply with the protocol and agree to return to the hospital for follow-up visits and examinations.

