### **Special Handling and Precautions:**

Stannic-117m pentetate (a conversion electron emitting pharmaceutical) should be received, used and administered only by persons authorized to handle radiopharmaceuticals in designated clinical settings. The receipt, storage, use, transfer and disposal of Stannic-117m pentetate are subject to the regulations and/or appropriate licenses of the competent official organization (Nuclear Regulatory Commission or the relevant regulatory authority of an Agreement State). Administration may be associated with potential risks to other persons from radiation or contamination from spills of bodily fluids such as urine, feces, or vomit. Therefore, radiation protection precautions must be taken in accordance with national and local regulations.

Stannic-117m pentetate should be handled by the user in a manner which satisfies both radiation

safety and pharmaceutical quality requirements. Appropriate aseptic precautions should be taken. In keeping with the As Low As Reasonably Achievable (ALARA) principle for minimization of radiation exposure, it is recommended to minimize the time spent in radiation areas, to maximize the distance to radiation sources, and to use adequate shielding.

Any unused drug product or materials used in connection with the dispensing or administration are to be treated as radioactive waste and should be disposed of in accordance with local regulations. Unused doses and waste may be destroyed following applicable agreement state and federal regulations for decay in storage for Stannic-117m pentetate following 10 half-lives.

Radiation protection precautions are to be followed in accordance with national and local regulations. Follow normal working procedures for the handling of radiopharmaceuticals and use universal precautions for handling and administration such as gloves and barrier gowns when handling blood and bodily fluids to avoid contamination.

**Patient Care Implications:** Fertile men study participants and their partners must abstain or use effective contraception (including barrier method) while receiving study treatment and for at least 6 months after the last dose of Stannic-117m pentetate. For at least 10-days after each dose, subjects should avoid close contact with others, should flush toilet several times after each use, and should avoid preparing food for others. Clothing soiled with patient fecal matter or urine should be washed promptly and separately from other clothing.

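### Section 10.5 requires partner pregnancies to be reported only to 90 days after the last dose, but Sections 3.1.17 and 8.1.1 require contraception for at least 6 months after it

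*Combined protocol and SAP*

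**What the plan says.** Section 10.5 (Pregnancy) opens by stating that "pregnancy as well as its outcome must be documented via" CTEP-AERS. That sentence carries no time limit. Two sentences later the section sets the limit for partners: a pregnancy is covered if it occurs "from the time of consent to 90 days after the last dose of study drug must be reported" and it is then followed for outcome, with newborns followed to 30 days of age. All participants are men, so the partner rule is the one that operates in this trial.

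Two other sections set the contraception period:

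- Section 3.1.17 (Eligibility Criteria) requires men to use contraception before the study, "for the duration of study participation, and 6 months after completion of Sn-117m-DTPA administration". It gives as reasons that the agent's fetal effects are not known and that contraception is needed "because radionuclides are known to be teratogenic".
- Section 8.1.1, under Patient Care Implications, requires abstinence or effective contraception "while receiving study treatment and for at least 6 months after the last dose of Stannic-117m pentetate".

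Section 3.1.17 also says that if a woman becomes pregnant or suspects it "while her male partner is participating in this study, she should inform her treating physician immediately". Section 6.5 sets follow-up at 12 months after the first dose or until death.

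**The concern.** The contraception requirement and the pregnancy-reporting requirement address the same hazard, but they stop at different times and the protocol does not explain the difference. A partner pregnancy in the fourth, fifth or sixth month after the last dose would mean that a precaution required by the protocol had failed, or had not been followed. A site reading 10.5 would have no duty to report it or to follow the infant. The agent is investigational and the protocol says its fetal effects are unknown, so the few pregnancies that might occur are the only source of such information in this trial.

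**Working it through.** The plan gives no figure to reproduce. The check sets the windows side by side and does date arithmetic.

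**Inputs**
- Reporting window after the last dose: 90 days (10.5).
- Contraception after the last dose: 6 months (3.1.17) or at least 6 months (8.1.1), taken as 180 to 184 days with 183 as the working value.
- Standard course: two doses 8 weeks (56 days) apart (6.1).
- Follow-up: 12 months, taken as 365 days, from the first dose (6.5).
- Half-life: 13.6 days (2.3), 13.9 days (Appendix J) or 14 days (8.1.1).

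**Gap after the last dose**
- Working value: 183 − 90 = 93 days; 93/183 = 51%.
- Range: 180 − 90 = 90 days (50%) to 184 − 90 = 94 days (51%).

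**Standard two-dose patient, counted from the first dose (day 0)**
- Mandatory reporting ends: 56 + 90 = day 146.
- Six months after the last dose ends: 56 + 183 = day 239.
- Follow-up ends: day 365.
- Uncovered share from first dose to the end of the six months: 93/239 = 39%.
- If the study-participation wording in 3.1.17 governs and participation means follow-up to 12 months, the gap is 365 − 146 = 219 days.

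**Residual activity of the last dose at day 90, physical decay only, 2^(−90/half-life)**
- 13.6 days: 1.02%
- 13.9 days: 1.12%
- 14 days: 1.16%

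**Does other text close the gap?**
- The opening sentence of 10.5 has no window, but the same paragraph then supplies one for partners.
- The instruction in 3.1.17 sends the partner to her own physician. It gives no route to CTEP and no follow-up of outcome.
- Section 10.3.3 lists a congenital anomaly as a serious outcome. Serious events more than 30 days after the last dose that are at least possibly related remain reportable, depending on grade and hospitalization, with no stated end date. This can capture an adverse outcome that comes to the site's attention. It does not capture the pregnancy itself or a normal outcome.

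None of these makes a pregnancy beginning after day 90 reportable.

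**The case against.** A reader might infer that pregnancies in the second half of the post-dose period go unreported. The documents do not support that. Section 10.5 sets what must be reported and does not bar a later report. The partner is asked to tell her physician throughout participation, which normally runs well past day 146. A possibly related congenital anomaly could still reach the sponsor as a serious adverse event. Section 10.5 also refers to NCI guidelines for further detail; these are not available here, so a longer window in them cannot be excluded. The supportable statement is that reporting is not required.

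A reader might also infer that the rule discards half of the fetal risk. That does not follow either. The half is a share of calendar days after the last dose. Reporting starts at consent and so covers the whole treatment period. The uncovered days come last, when about 1% of the last dose's activity remains. No section defines a fetal-risk period or says that reporting must match contraception. A contraception margin longer than the reporting window could be deliberate, but the protocol does not say so.

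The practical yield is also small: the trial has 25 men with castrate testosterone and mandatory contraception. This limits the importance of the point but does not reconcile the sections.

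**Conclusion.** The mismatch is real and lies in the current operative text. Pregnancies beginning from day 91 to about day 183 after the last dose (90 to 94 days, depending on how six months is counted) fall inside the required contraception period but outside the mandatory reporting and outcome follow-up. The gap is longer if 3.1.17 is read as running to the end of study participation. The same gap follows the last dose of a retreatment course.

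This is a minor safety-reporting correction. Few if any events are expected, and the primary endpoint, the two-stage design and its error rates are unaffected. The conclusion assumes that sites apply the explicit window in 10.5 and that the cited NCI guidelines do not override it.

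**What to change.** Extend the reporting and outcome follow-up window in 10.5 to cover the whole contraception period that the protocol requires, which on the present text is at least 6 months after the last dose, including after retreatment. State that period in the same words in 3.1.17, 8.1.1 and 10.5. Replacing 90 days with a flat 6 months in 10.5 may not be enough, because 3.1.17 also ties contraception to study participation. The sponsor must settle how the 3.1.17 and 8.1.1 wordings fit together and then carry the result into 10.5. If the consent form, which is not available here, states a reporting window, it should be matched.

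The cost is an edit to three sections and a slightly longer reporting duty. For a standard two-dose patient, six months ends near day 239, inside the 12-month follow-up. With the full 8-week delay allowed in Section 7 it ends near 56 + 56 + 183 = day 295, still inside. A retreated patient whose last dose falls more than 365 − 183 = 182 days after the first would pass the one-year mark before the six months end. Section 6.5 then provides only for collecting dates of death, so a brief contact to ask about partner pregnancy would be needed.

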## 10.6 Secondary Malignancy

A *secondary malignancy* is a cancer caused by treatment for a previous malignancy (e.g., treatment with investigational agent/intervention, radiation or chemotherapy). A secondary malignancy is not considered a metastasis of the initial neoplasm.

CTEP requires all secondary malignancies that occur following treatment with an agent under an NCI IND/IDE be reported expeditiously via CTEP-AERS. Three options are available to describe the event:

- Leukemia secondary to oncology chemotherapy (e.g., acute myelocytic leukemia [AML])
- Myelodysplastic syndrome (MDS)
- Treatment-related secondary malignancy

Any malignancy possibly related to cancer treatment (including AML/MDS) should also be reported via the routine reporting mechanisms outlined in each protocol.

## **10.7 Second Malignancy**

A second malignancy is one unrelated to the treatment of a prior malignancy (and is **NOT** a metastasis from the initial malignancy). Second malignancies require **ONLY** routine AE reporting unless otherwise specified.

## 11. STUDY CALENDAR

Baseline evaluations are to be conducted within 4 weeks prior to start of protocol therapy. Scans and x-rays must be done  $\leq$  8 weeks prior to the start of therapy. In the event that the patient's condition is deteriorating, laboratory evaluations should be repeated within 48 hours prior to initiation of the next cycle of therapy.

Visit dates and scans can be within  $\pm$  7 days of planned dates. Study treatment must start within 30 days of registration.

	Pre-study	Cycle 1 (8 weeks or 56 days)					Cycle 2 (8 weeks or 56 days)					Post-treatment					Follow-up a	Off-study visit	
		W1	W2	W4	W6	W8	W1	W2	W4	W6	W8	18 weeks	20 weeks	22 weeks	24 weeks	26 weeks	28 weeks		
Sn-117m-DTPA		A					A											A*	
Informed consent	X																		
Demographics	X																		
Medical History	X																		
Pain medication**	X	X	X	X	X	X		X	X	X	X		X		X		X	X (every 3 months)	X
Physical Exam	X	X		X	X			X		X		X		X		X		X	X
Vital signs	X	X		X	X			X		X		X		X		X		X	X
Height	X																		
Weight	X	X		X	X			X		X		X		X		X		X	X
Performance status	X																	X	
CBC/diff, platelets	X	X	X	X	X	X i		X	X	X	X		X		X		X	X	X
Serum chemistry b	X	X	X	X	X	X i		X	X	X	X		X		X		X	X	X
PSA	X			X	X			X		X		X		X		X		X	X
Adverse Events		X-----X																	
Patient-reported pain intensity scale and analgesic use c	X		X	X	X	X		X	X	X	X	X	X	X	X	X	X	X	X
Patient-reported CTCAE d			X	X	X	X		X	X	X	X	X	X	X	X	X	X	X	X
Sn-117m-DTPA dosimetry (optional) e		X	X	X	X														
Urine collection for urinalysis f	X						X												

NCI Protocol #: 10437  
 Version Date: January 10, 2022

	Pre-study	Cycle 1 (8 weeks or 56 days)					Cycle 2 (8 weeks or 56 days)					Post-treatment					Follow-up a	Off-study visit	
		W1	W2	W4	W6	W8	W1	W2	W4	W6	W8	18 weeks	20 weeks	22 weeks	24 weeks	26 weeks	28 weeks		
Radiologic evaluation (CT of abdomen/pelvis and bone scan) and chest X-ray g or PSMA PET CT scan	X					X					X				X			X (every 3 months)	
Research blood for genomic whole exome sequencing (mandatory when archival tissue or slides are submitted)	X																		
Research blood for exploratory studies (optional) h	X					X h					X h				X				
Archival tissue for genomic sequencing and exploratory PLK1 stain (optional)	X																		

A: Sn-117m-DTPA: 20 mCi/70 kg (0.28 mCi/kg) slow IV injection over 10 min on C1D1 and C2D1

\*Patients can be retreated if pain recurs within 6 months after 16-week pain observation period

a: Follow-up visit evaluation. Every 3 months or as clinically indicated up to one year from the first dose injection or disease progression

b: Albumin, ALP, total bilirubin, bicarbonate, BUN, calcium, chloride, creatinine, glucose, LDH, sodium, potassium, total protein, SGOT [AST], SGPT [ALT].

c: Pre-treatment daily baseline pain and analgesic use for 7 days (at least 4 out of 7 days) is required before treatment initiation. Patients will be asked to report their pain at its worst in the last 24 hours and analgesic use (stable/reduced/increased) by digital version every 2 weeks through Week 28, followed by routine clinic follow up or when they experience new pain during off-visit. **A full short version of brief pain inventory (BPI) will be asked at baseline, after Cycle 1, after Cycle 2, and at Week 24.**

d: PRO-CTCAE survey items will be assessed by digital instruments. Beginning at Week 28, surveys are requested every 3 months for 6 months after the last study treatment administration.

e: Serial DTPA dosimetry scans (optional) will be obtained at 1 hour, 4 hours (or within 4-6 hours), 24 hours (or within 16-24 hours), 48 hours (or within 36-48 hours), 72 hours (or within 60-72 hours), 1 week (+/2 days), and 4 weeks (+/2 days) post-infusion. The dosimetry scan will only be performed with first cycle of injection.

f: Urine collection for urinalysis will be collected at the indicated time points or as clinically indicated to monitor for microscopic or macroscopic hematuria as part of genitourinary toxicity monitoring.

g: Imaging: Follow up tumor response will be evaluated by CT scan of abdomen and pelvis, bone scan and chest X-ray. If Chest X-ray shows abnormal or clinically symptomatic, then CT chest should be obtained. Follow-up scans at every 8 weeks will be performed as clinically indicated, per institutional standards. PSMA PET CT scan at baseline is also acceptable.

*NCI Protocol #: 10437*

*Version Date: January 10, 2022*

h: Blood collections for research during Cycles 1 and 2 should be collected on the last day of each cycle.

i: CBC and serum chemistry should be performed 1 week before the start of Cycle 2.

\*\* Study coordinator/research nurse will require to ask pain medications list including names, dosage and frequency and also is required to fill out pain medication list form during every clinic visit.

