### 5.10.2.2.2 Timing of Assessment

Pain at baseline and analgesic use (pre-treatment, Week 0) will be measured via serial (daily) assessments in a 7-day run-in period. Patients will be considered evaluable if they complete assessments on  $\geq 4$  days within the 7-day run-in period. During treatment, pain and analgesic use will be measured every 2 weeks through Week 28, followed by routine clinic follow-up until 1 year or when patients experience new pain. Complete pain assessments via the full BPI-SF (Appendix D) will be collected at baseline, after Cycle 1, after Cycle 2, and at Week 28. Pain assessments will be halted at the patient's request or if the patient discontinues study treatment for reasons other than disease progression.

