## 6.5 Duration of Follow-Up

Patients will be followed every 2 weeks during treatment (16 weeks), then every 4 weeks until Week 28, and then every 3 months or as clinically indicated for 12 months after the first Sn-117m-DTPA dose or until death, whichever occurs first. After the 1-year follow-up period, dates of death will be collected for all patients until the final patient completes his 1-year follow-up. Patients removed from study for unacceptable adverse event(s) will be followed until resolution or stabilization of the adverse event.

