## 9.4 Analysis of Secondary Endpoints

Secondary endpoints will be summarized depending on data type. Categorical endpoints will be summarized by frequency and percent. Continuous variables will be summarized by mean and standard deviation at each assessment time point. Time-to-event endpoints will be summarized by Kaplan-Meier Methods. Safety and toxicity will be assessed through the frequency and percent of adverse events (AEs), serious adverse events (SAEs), and adverse events of special interests (AESIs). Toxicity will be assessed using Common Terminology Criteria for Adverse

Events v 5.0 (CTCAE). Safety and toxicity will also be assessed by patient-reported outcomes and adverse events (PRO-CTCAE) captured by digital instruments during treatment and 8 weeks after the last injection to monitor for acute toxicity and every 2-4 weeks for 6 months post-therapy for monitoring of long-term toxicity. CTCAE grades for the corresponding time period will be presented in conjunction with PRO-CTCAE scores. PSA and ALP response rates will be calculated for each of the above defined categories with the corresponding confidence intervals. *Post-hoc* analysis on PSA and ALP levels may be conducted to explore possible trends in PSA and ALP levels. Time to the first symptomatic skeletal event will be analyzed using the Kaplan-Meier method. Estimation and confidence intervals for the median time to first symptomatic skeletal event will be provided. Patients who did not have a symptomatic skeletal event will be censored at the last study visit. PFS will be analyzed in a similar manner as the time to first skeletal event. Patients who did not have observed clinical progression will be censored at the last assessment.

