#### 9.4.3 Time to First Symptomatic Skeletal Event

The time from study enrollment to 1) the first use of external-beam radiation therapy to relieve skeletal symptoms, 2) new symptomatic pathologic vertebral or non-vertebral bone fractures, 3) spinal cord compression, or 4) tumor-related orthopedic surgical intervention will be evaluated.

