#### 9.4.8 Clinical Progression-Free Survival

Clinical PFS will be calculated from the time of study enrollment until disease progression, which is defined as 1) symptomatic progression (increasing pain from a metastatic lesion); 2) progression of bone lesions assessed per PCWG3 criteria; or 3) progression of soft-tissue lesions

assessed per RECIST v1.1 criteria. PSA progression without progression on bone lesions nor symptomatic is not considered as clinical progression. Clinical PFS will be censored if clinical progression is not observed.

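### After Week 28 the study calendar lets follow-up end at progression while Section 6.5 runs it to 12 months, so censoring of skeletal events is unsettled and plausibly informative

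*Combined protocol and SAP*

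**What the plan says.** Two places set the end of follow-up.

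- **Section 6.5** continues visits after Week 28 "every 3 months or as clinically indicated for 12 months after the first Sn-117m-DTPA dose or until death, whichever occurs first". Progression is not an end point. The section adds that "dates of death will be collected for all patients until the final patient completes his 1-year follow-up".
- **Section 11, note a**, attached to the Follow-up column that comes after the Week 28 column, runs the visits "up to one year from the first dose injection or disease progression". It does not say that the earlier of the two applies.

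Three passages in Section 9.4 give the difference its statistical weight.

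- Time to first symptomatic skeletal event is analysed by Kaplan-Meier, and Section 9.4 states: "Patients who did not have a symptomatic skeletal event will be censored at the last study visit".
- Section 9.4.3 counts as an event "the first use of external-beam radiation therapy to relieve skeletal symptoms".
- Section 9.4.8 counts as progression "symptomatic progression (increasing pain from a metastatic lesion"), alongside bone and soft-tissue progression.

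**The concern.** Kaplan-Meier assumes that a censored patient has the same future risk as those still followed. Under note a the trigger for censoring is progression, and one route to progression is worsening pain at a metastatic lesion. That is a plausible step towards palliative radiation, which is itself a skeletal event. A patient after Week 28 could therefore be declared progressed, leave the visit schedule, be censored at that visit, and be irradiated shortly afterwards without the event being counted.

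The endpoint at stake is secondary objective 1.2.4. If skeletal risk rises after progression, the error runs one way, towards fewer events. Sites could also differ in which rule they follow, and with 25 patients a handful handled differently would be noticeable. Laboratory tests, examinations and non-serious late adverse events due at the same visits could be missed as well.

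**Working it through.** **Text.** Setting the rules side by side:

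| | Section 6.5 | Note a |
|---|---|---|
| End of scheduled follow-up | 12 months from first dose, or death | one year from first dose, or progression |
| Earlier-of-the-two stated | yes | no |
| Part of schedule covered | whole schedule | column after Week 28 |
| Last visit of an event-free progressor | about month 12, or the last before death | progression visit, or Week 28 if progressed earlier |

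The last row is where Section 9.4 censors.

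**Size.** The plan states no progression rate, no skeletal-event rate and no precision target for this endpoint, so there is no plan figure to reproduce. The following is an illustration. All of its rates are assumptions:

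- exponential time to progression, median m = 4, 6 or 9 months, so μ = ln 2 / m;
- skeletal-event hazard before progression λ = -ln(0.80)/12 = 0.01860 per month, that is, 20% at 12 months without progression;
- hazard after progression kλ, with k = 1, 2 or 3;
- note a acting only after Week 28, W = 28/4.345 = 6.444 months;
- no deaths and no other dropout.

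Event-free probability with full follow-up:

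S(t) = e^(-(λ+μ)t) + [μ/(μ+λ-kλ)] × e^(-kλt) × [1 - e^(-(μ+λ-kλ)t)]

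Under note a, nobody is censored for progression before W. After W only unprogressed patients remain at risk, with hazard λ, so the Kaplan-Meier incidence at 12 months tends to 1 - S(W) × e^(-λ(12-W)). The proportion of patients with an event that is seen is [1 - S(W)] + e^(-(λ+μ)W) × [λ/(λ+μ)] × [1 - e^(-(λ+μ)(12-W))].

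Worked case, m = 6 and k = 2 (μ = 0.11552, μ+λ-kλ = 0.09693, ratio 1.1918):

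- S(12) = 0.2000 + 1.1918 × 0.6400 × 0.6875 = 0.7244, so true incidence is 27.6%.
- S(W) = 0.4213 + 1.1918 × 0.7869 × 0.4645 = 0.8570.
- Kaplan-Meier reads 1 - 0.8570 × 0.9018 = 22.7%.
- Seen: 0.1430 + 0.4213 × 0.1387 × 0.5253 = 0.1737. Unseen: 1 - 0.1737/0.2756 = 37%.

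All nine cases, with note a acting only after Week 28:

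| Median progression | k | True 12-month incidence | Kaplan-Meier reads | Events unseen |
|---|---|---|---|---|
| 4 months | 1 | 20% | 20% | 34% |
| 4 months | 2 | 30% | 24% | 42% |
| 4 months | 3 | 38% | 27% | 44% |
| 6 months | 1 | 20% | 20% | 28% |
| 6 months | 2 | 28% | 23% | 37% |
| 6 months | 3 | 34% | 25% | 41% |
| 9 months | 1 | 20% | 20% | 22% |
| 9 months | 2 | 26% | 22% | 31% |
| 9 months | 3 | 31% | 24% | 35% |

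A simulation of 400,000 patients per case agrees to within half a percentage point.

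The k = 1 rows separate two effects. With an unchanged hazard the estimate is unbiased and only information is lost. The censoring biases the estimate only if risk changes after progression.

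**The case against.** The strongest reply is that Section 6.5 is the dedicated follow-up section, is explicit, and is nowhere said to yield to a calendar footnote whose own wording is loose. Other provisions also carry on past progression, which suggests note a is the outlier. The trial has one arm, and time to first skeletal event is summarised without a hypothesis or decision rule, so no trial decision turns on it. All of this is fair. It limits the point to a conflict that must be settled and to sites that follow the calendar. It does not remove the conflict, because staff can be expected to schedule visits from the calendar.

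A reader might also infer more than the documents support:

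- **That post-progression data are lost.** This would need note a to override Section 6.5, and nothing says so.
- **That follow-up stops at progression whenever it occurs.** Note a is attached to the column after Week 28, and visits up to then stand. If follow-up did stop at any progression, the same assumptions would leave 33-77% of events unseen. The calendar as laid out does not support that reading.
- **That patient-reported outcomes are cut off.** Section 5.10.2.2.2 says: "Pain assessments will be halted at the patient's request or if the patient discontinues study treatment for reasons other than disease progression". That implies progression does not halt pain reporting. PRO-CTCAE runs to 12 months from first dose in Section 2.4.6 and to 6 months after last treatment in note d. Those durations disagree with each other, which is a separate matter, but neither is tied to progression.
- **That late toxicity goes unrecorded.** Related serious events beyond 30 days (Section 10.3.3, footnote 1) and secondary malignancies (Section 10.6) are reportable with no progression cut-off. Patients removed for unacceptable adverse events are followed to resolution or stabilisation (Section 6.5). What remains exposed is scheduled laboratory tests, examinations and non-serious late events.
- **That the main results are biased.** The primary endpoint needs at most 28 weeks. Progression-free survival has already had its event at progression. Deaths are collected for everyone.

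**Conclusion.** The inconsistency is real and should be corrected. Where note a is applied, event-free patients are censored at progression, or at Week 28 if they progressed earlier. The plan's own definitions of progression and skeletal event make that censoring plausibly informative. If the hazard doubles or triples after progression, 12-month Kaplan-Meier incidence would read about 22-27% against a true 26-38%, with 31-44% of events unseen. If the hazard is unchanged there is no Kaplan-Meier bias, but 22-34% of events are still unseen.

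These figures rest wholly on assumed rates and on every site applying note a. With mixed practice the effect would be smaller and would vary by site. The rise in risk after progression is also an assumption, though the overlap in definitions makes it reasonable. The consequence is a possibly understated secondary estimate and some missing routine safety data.

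**What to change.** 1. Reword note a to agree with Section 6.5: follow-up for skeletal events and adverse events continues to 12 months from first dose or death, regardless of progression.
2. In Section 9.4, replace censoring at the last study visit with censoring at the last skeletal-event assessment under that follow-up.

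The patient-reported outcome schedules need no change for this purpose. The cost is wording in two places, because Section 6.5 already schedules the visits. The change should be made before patients reach the follow-up column, since skeletal events missed after progression may not be recoverable later.
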